4.12 Post-Assessment Questions/Label Comprehension

Participants will answer a series of questions after they complete the OraQuick® HIV Self-Test assessment and Interpretation of Results – Mock Devices. Questions related to warnings and precautions and the key following information is included in the post-questionnaire:

[figure not shown]
- What would you do next if your test results were negative?
- What would you do next if your test results were positive?
- What would you do if your test results were invalid?
- Did you use the Instruction sheet to help you complete the test? If No, please explain
- Was the device easy to use? If No, please explain
- Are you confident you could perform this test on your own? If No, please explain
- Would you use this test again if it were available to you? Would you recommend this test to others?
- How long after ingesting food or drink should you wait to test?

CONFIDENTIAL Page 21 of 45

4.13 Confirmatory Procedures

All self-test results will be confirmed using a HIV-1/HIV-2 Antigen/Antibody Combo Test (Comparator Method "CM") performed on venous blood plasma at the central laboratory. A venous whole blood specimen will be collected from all study participants and sent to a central laboratory within 72 hours to establish the CM and any further confirmatory results for all participants. An appointment will be scheduled with the participants to return to the study site to collect their standard-of-care testing result. The Laboratory Confirmatory testing decision tree is presented below.

Laboratory Testing Procedure for HIV EDTA Blood and Plasma

CONFIDENTIAL Page 22 of 45

Version 1: 13-Jul-2021

All clinical laboratory testing will be performed using a 4th generation HIV-1/HIV-2 Antigen/Antibody Combo Test.

4.14 Additional Procedures and for Study Participants with Preliminary Positive Self-Test Results

Any study participant who has a preliminary positive OraQuick® HIV Self-Test result, as determined by the trained Observer's interpretation of the study participant's self-test will be counseled by the appropriate study staff regarding the meaning of their result consistent with current guidelines and local standard operating procedures (SOPs) for HIV counseling knowing that this test is investigational and that their laboratory results will be the official reportable results.

4.15 Additional Procedures for Study Participants with Negative Results

Any study participant who has a negative OraQuick® HIV Self-Test result, as determined by the trained Observer's interpretation of the study participant's self-test will be counseled by the appropriate study staff regarding the meaning of their result consistent with current guidelines knowing that this test is investigational and that their laboratory results will be the official reportable results.

4.16 Compensation for Study Participants

Participants will be compensated for their time and effort in this study. The compensation amount will be up to \$75 in total. On the 1st visit to the clinic and upon completion of the main study procedures (Appendix H), the participant will receive \$50 and if they return in two weeks for their laboratory test result, they will receive the remaining \$25.

5. QUALITY CONTROL AND ASSURANCE

Quality Control on the study will be done following the Standard Operating Procedures developed for the study and those generic to the organization. The Research Manager assumes overall responsibility for ensuring all procedures are adhered to and quality controlled.

5.1 Training

Prior to the study, the Principal Investigator will ensure that all study staff are trained on the protocol and all study procedures.

5.2 Trained Researcher/ Observer Responsibilities

The site will provide a minimum of two (2) trained Observers responsible for enrolling eligible participants, collecting samples, and running, interpreting, and documenting the results of the OraQuick® HIV Self-Tests. Prior to the beginning

CONFIDENTIAL Page 23 of 45

of the study, all trained observers will receive appropriate training that covers study procedures, as well as, instructions for performing the test.

Version 1: 13-Jul-2021

5.3 Study Monitoring

The study will be monitored by the Research Manager or designate to ensure compliance with local laws and regulations and to ensure data quality. This person has the obligation to follow the study closely and in doing so, will routinely visit the site(s) at periodic intervals, to assess study status and review study procedures and applicable documents. Site visits can be in person or virtual, depending on any pandemic-related restrictions in place during the study period. They will also maintain necessary telephone and email contact. The monitor will maintain current personal knowledge of the study through observation, review of study records and source documentation, and discussion of the conduct of the study with the Principal Investigator and study staff.

6. DATA ANALYSIS

6.1. Data Management Processes

All participant data will be collected using tablets on the survey software tool Qualtrics. All tablets are password-protected. Qualtrics software stores participant data on local, secure servers in Toronto. Only the St. Michael's Hospital Research staff will be able to access the data from the Qualtrics servers. This data will be password-protected. Data will then be downloaded and saved to secure encrypted servers at St. Michael's Hospital for further analysis. Data monitoring will be performed daily by the St. Michael's Hospital Research staff. All data will be stored on secure servers at St. Michael's Hospital until the data analysis stage of the project. All study data will be tabulated using appropriate software and methods. Data will be archived by the study Sponsor and maintained for 7 years after the end of the study.

6.2. Data Reporting

Data analysis and reporting will be performed by the Research Manager and study consultants. A research report will describe the study area, the study population, the execution of the research, and present the study results. The report will present both qualitative and quantitative discussions of the outcomes of the study.

6.3. Primary Analysis

The primary analyses will be sensitivity and specificity of study participants' self-interpreted self-test results with the OraQuick[®] HIV Self-Test versus the HIV status as determined by the 4th generation EIA and confirmatory testing if necessary. The 95% confidence interval will also be determined by the Wilson Score Method.

CONFIDENTIAL Page 24 of 45

- Sensitivity = [TP / (TP + FN)] x 100, where
 - TP (true positive) is positive OraQuick® HIV Self-Test in agreement with HIV positive status and

Version 1: 13-Jul-2021

- FN (false negative) is negative OraQuick® HIV Self-Test discordant with HIV positive status.
- Specificity = [TN / (TN + FP)] x100, where
 - TN (true negative) is negative OraQuick® HIV Self-Test in agreement with HIV negative status, and
 - FP (false positive) is positive OraQuick® HIV Self-Test discordant with HIV negative status.

Invalid and unknown/unsure results and participants with inclusion/exclusion violations will be excluded from the sensitivity and specificity analysis. All excluded participant results will be documented with the reason why.

6.4. Secondary Analysis

Secondary efficacy analysis may be performed for the following sub-groups listed below. If conducted, it will include descriptive statistics of the sensitivity and specificity analyses among various subgroups for each specificity and sensitivity for the following factors:

- Age.
- Language capabilities (self-reported).
- Educational level.
- Literacy level
- Risk Factors
- Risk Populations

Additional secondary efficacy analyses will include the descriptive statistics of the following:

- Observational Ratings of Study Participant Self-Test Performance
- Trained User's (Observer) Interpretation of Study Participants Self-Test Result
- Participant Mock Study Results

6.5. Demographics

The following will be summarized with descriptive statistics:

- Demographic Data
- Background Data
- Medical History

CONFIDENTIAL Page 25 of 45

6.6. Error and Failure Rates

Specific critical and non-critical steps are identified from the OraQuick® HIV Self-Test Instructions for Use.

Version 1: 13-Jul-2021

Critical errors occur when participants perform operational errors during the assay which could potentially invalidate the results, such as specimen collection errors or terminating the process before completion.

Non-critical errors occur when participants perform errors that may deviate from the Instructions for Use but do not invalidate results. The successful completion of tasks will be evaluated as a percentage of the overall process, with all critical errors identified.

Errors are defined in the table below:

Task	Category (critical / non-critical)
Reads the instructions for use	Critical
Able to find the test tube packet	Non-Critical
Remove the test tube from the packet	Critical
Remove the cap from the test tube	Critical
Placed the test tub in the test stand (holder)	Critical
Able to find the test stick packet	Non-Critical
Remove the test stick from the packet	Critical
Touching the flat pad	Critical
Correctly collected the oral fluid sample	Critical
Placing the device in the test tube (developer vial)	Critical
Read the results within the 20-40 minute window	Critical

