2. STUDY OBJECTIVES

The primary objectives of this study will be to:

- 1) Evaluate the device performance, i.e. sensitivity and specificity, compared to laboratory reference testing
- 2) To document if intended users (non-professional "lay users"), can successfully perform the steps to use the OraQuick® HIV Self-Test, without product familiarization or demonstration (accuracy/usability)
- 3) To document if intended users, (non-professional "lay users"), can successfully interpret contrived strong positive, weak positive, negative, and a range of invalid results (test results interpretation) and
- 4) To document if intended users can understand the key messages in the labeling (label comprehension).

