3.4. Study Description

Usability

The self-test portion of the study will be performed on consenting persons (referred to as participants) and will include recruitment of participants who have consented to be tested for HIV as per the test procedures outlined.

The participant will be evaluated for the self-test process success or difficulty by a silent, non-interacting trained healthcare professional / researcher (Observer) in the same room. Overall processes include self-test Usability (observation to determine if participants perform all critical steps correctly), Results Interpretation (confirmation by observer to determine if participant interprets test results correctly), and Label Comprehension (questionnaire to determine that the participant is aware of test limitations and what to do following the test result). Successful completion of these tasks will be evaluated as a percentage of the overall process, with all critical errors identified.

Each participant will obtain an oral fluid specimen and perform the test, including result interpretation, according to only those materials provided with the OraQuick® HIV Self-Test (e.g. instructions for use).

Each self-test will be observed by trained healthcare professional/ researcher (referred to as Observers). The Observer does not tutor or interact with the participant conducting the self-test but notes errors and other observations about the participant.

CONFIDENTIAL Page 12 of 45

The Observer also interprets the test result, immediately after the participant and within the validated reading time stated in the instructions for use and records the result separately.

Version 1: 13-Jul-2021

All participants will have a venous blood sample taken (typically from the forearm; up to 7mls or about 1.5 tablespoons) and sent to a local provincial laboratory for HIV EIA testing. The laboratory portion of the study will conduct Comparator Method ("CM") testing on plasma from venous blood samples collected from study participants with Health Canada licensed HIV-1/HIV-2 combination antigen/antibody test that is in routine use in the participating local laboratories. Results of all laboratory testing will be shared with the intended use sites since the lab test will serve as the standard of care test.

Sites will be using their local lab or arrange to have samples sent to a lab that uses the same comparator assay.

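### No planned summary gives the share of participants who make no critical error, although the protocol describes usability (primary objective 2) in those terms

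*Combined protocol and SAP*

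**What the plan says.** Section 2 lists four primary objectives. The second is to document whether untrained lay users manage the steps of the test.

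Section 3.4 gives usability its content: "observation to determine if participants perform all critical steps correctly". This is a statement about each participant, and it is all-or-none. The same paragraph then gives the scoring rule: "Successful completion of these tasks will be evaluated as a percentage of the overall process, with all critical errors identified". The process it refers to is wide ("Overall processes include self-test Usability", and results interpretation and label comprehension as well).

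Section 6 deals with usability in two places:

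- Section 6.6 repeats the scoring rule: "The successful completion of tasks will be evaluated as a percentage of the overall process, with all critical errors identified". It defines critical errors as those that could invalidate the result, naming specimen collection errors and early termination as examples. It then classifies 11 tasks.
- Section 6.4 lists "Observational Ratings of Study Participant Self-Test Performance" among the secondary descriptive analyses, without naming a summary measure.

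Section 6.3 does not mention usability: "The primary analyses will be sensitivity and specificity". The only interval method in the plan is stated there: "The 95% confidence interval will also be determined by the Wilson Score Method".

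**The concern.** The protocol separates critical from non-critical tasks because only a critical error threatens the validity of the result. For objective 2, the useful figure is therefore how many lay users got through the test without one. A percentage of tasks completed is a different quantity. It counts the 2 non-critical tasks, and it averages over tasks rather than people. One participant failing several steps and several participants failing one step each can give the same score.

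Step-by-step rates do not close the gap, because they leave open whether the failures fall on the same people. A high process percentage could therefore be reported for objective 2 while the share of users who met the section 3.4 description stays unstated. With no acceptance threshold in the documents, the reported figure is itself the result for this objective, so its form should be settled before the data are seen.

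**Working it through.** **Inputs.** The 6.6 table has 11 tasks, 9 critical and 2 non-critical (finding the tube packet and finding the stick packet). Section 4.1 has all 900 participants assessed for usability. The documents give no step success rates, usability target or usability sample-size calculation, so there is no stated figure to reproduce. The 95% and 99% rates below are assumptions for illustration.

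**One constraint.** Two critical failures exclude each other: a participant who never takes the stick out of its packet cannot be seen touching its pad. One person can therefore fail at most 10 of the 11 tasks.

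**A. What a pooled 95% implies.** Tasks: 900 × 11 = 9,900. Failed tasks: 9,900 × 0.05 = 495.

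| How the 495 failures fall | Calculation | Share with no critical error |
|---|---|---|
| One critical error in each of 495 people | 1 − 495/900 | 45.0% |
| Every step at 95%, independent | 0.95^9 | 63.0% |
| Clustered in as few people as possible | 495/10 = 49.5, so 50 people; 850/900 | 94.4% |

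The independence row ignores the exclusion. Allowing for it, the two linked steps are both passed with probability 1 − 0.05 − 0.05 = 0.90, and 0.95^7 × 0.90 = 62.9%, so about 63% stands.

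The share would be higher if failures fell on the non-critical tasks. By count alone they could all do so, since 495 is below 2 × 900 = 1,800, and the share would then be 100%. If not finding a packet also means not removing its contents, which is a critical task, everyone with a failure has a critical one and the ceiling returns to 94.4%.

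**B. What step-by-step rates imply.** Let each of the 9 critical steps have success rate p.

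- Lowest share, with no two errors in the same person: 1 − 9(1 − p).
- Highest share, with errors overlapping as far as possible but the two exclusive ones in different people: 1 − 2(1 − p).

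| p | Lowest | Highest |
|---|---|---|
| 95% | 1 − 9 × 0.05 = 55% | 1 − 2 × 0.05 = 90% |
| 99% | 1 − 9 × 0.01 = 91% | 1 − 2 × 0.01 = 98% |

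Neither the pooled score nor the step rates fix the share. It has to be counted from participant-level records.

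**C. Precision of the added summary.** Wilson 95% intervals with n = 900 are 59.8% to 66.1% for 567/900 (63%) and 92.8% to 95.8% for 850/900 (94.4%).

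**The case against.** The strongest reply is that section 6 does follow section 3.4. The scoring sentence in 6.6 is almost the same as the one that closes the usability paragraph in 3.4, and the phrase about performing all critical steps is a parenthesis describing what observers look for, not a declared endpoint. Objective 2 asks only for documentation, critical errors are to be identified, and 6.4 plans descriptive statistics of the ratings. Step rates with critical errors listed are a legitimate description. An all-or-none composite gives not reading the instructions the same weight as faulty specimen collection.

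Much of this stands. A reader might infer that section 6 drops the usability criterion altogether. It does not: the scoring rule, the task classification and the reporting of critical errors are all carried over, and the share could be built from the data to be collected. The equal weighting is a real limitation, which is why the step rates should stay beside the new figure.

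A reader might also infer a data-collection gap, because the ratings in section 4.9 have no item for the 20–40 minute reading window. The documents do not support that. Section 4.9 has observers record the start and read times, and the content of the observer form (Appendix E) is not shown.

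The percentage could instead mean the share of people completing the whole process. That reading comes close to the wanted figure but still counts the 2 non-critical tasks. Defining the percentage is a clarification, and on the natural reading it would not supply the missing share.

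**Conclusion.** The concern holds as a gap in the planned summaries. The plan describes usability as performing all critical steps correctly and collects what appears to be the necessary data, but no analysis reports the share of participants who did so. A pooled 95% could accompany anything from 45% upward. Step rates of 95% on every critical task leave a range of 55% to 90%, and rates of 99% leave 91% to 98%. These figures rest on assumed rates and on counting a touched pad as an error when it is observed. They show how loosely the measures are tied and do not forecast results.

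A reader might go further and conclude that the study could wrongly pass on usability, or that 900 participants is the wrong number. Neither follows. The documents set no usability threshold, and sections 4.1 and 6.7 take the sample size from regulatory guidance, not from a calculation. No stated figure is in error. This is a cheap improvement that should be made before analysis.

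**What to change.** In 6.6, add for objective 2 the proportion of participants who attempted the self-test and made no critical error across the 9 critical tasks, with a 95% Wilson interval as in 6.3. State three scoring rules with it:

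- Derive the 20–40 minute item from the recorded start and read times.
- Score touching the flat pad as an error when observed.
- Count early termination as a critical error, as 6.6 already does; section 4.9 documents tests that could not be completed.

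Report the step-by-step rates alongside, and keep the process percentage as descriptive with its numerator and denominator stated.

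The cost is a few sentences in 6.6, with no added participants or visits. Check that the observer form holds each item by participant. The downsides are a possibly less favourable headline figure and the equal weighting of critical tasks within the composite.

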6.7. Sample Size

Sample size for this study was based on the Health Canada Guidance Document: Guidance for Manufacturers of Human Immunodeficiency Virus (HIV) Rapid Diagnostic Tests (RDTs) for use at the Point of Care or for Self-Testing. ¹⁴ The sample size requirements for a near-patient study with untrained self-testers is a minimum of 900 laypersons with unknown HIV status, including 400 persons at risk for HIV infection (e.g. IDU, MSM, etc.). To assess the ability of untrained self-testers to correctly interpret a variety of pre-made mock (contrived) devices test results, a minimum of 400 persons are required. A minimum of 200 self-testers are required to assess for label comprehension. ¹⁴

CONFIDENTIAL Page 26 of 45

It should be noted that the OraQuick ADVANCE® HIV-1/2 Rapid Antigen Test is not intended for use by individuals that are known to be HIV positive.

7. OBLIGATIONS OF THE INVESTIGATOR

7.1 Retention of Records

Data collected throughout the duration of the study will be stored for 7 years on secure servers at St. Michael's Hospital. After this time period, all data will be destroyed by the SMH Study Team. This storage strategy is compliant with St. Michael's Hospital Data Security to store/encrypt all data. Electronic data will be securely and confidentially stored and will not contain any identifying information. Other sites that obtained data though data transfer will also destroy any data after 7 years of study completion.

If an investigator moves, withdraws from an investigation, or retires, the responsibility for maintaining the records may be transferred to another person, who is willing to accept the responsibility.

7.2 Device Accountability

The principal investigator or his/her designees will maintain accurate records of all investigational assays/devices used in each study performed under this protocol. Damaged, dropped, or otherwise destroyed devices will be noted and documented on the device accountability form.

7.3 Protocol Amendments

Amendments to the protocol must be submitted in writing to the REB for approval before participants are enrolled into an amended protocol, except where it is necessary to eliminate an immediate hazard to participants or where the changes involve only logistical or administrative aspects of the clinical study. This should be fully documented. Protocol amendments must be prepared by the Principal Investigator responsible for the study and reviewed and approved according to local authorities and REB/EC. With the exception of administrative changes, any modifications or additions to this study protocol require a justified, written protocol amendment that must be approved by the Principal Investigator, local authorities, and REB/EC. Amendments potentially affecting the safety of study participants, the scope of the investigation or the scientific quality of the study, require approval. A copy of the written approval must be maintained by the Principal Investigator.

Examples of amendments requiring such approval are:

- A significant change in the study design
- An addition or deletion of a test procedure for safety monitoring

These requirements for approval should in no way prevent any immediate action from being taken by the investigator or the sponsor in the interests of preserving the safety of all study participants included in the trial. If an immediate change to the protocol is deemed necessary by the investigator and is implemented by

CONFIDENTIAL Page 27 of 45

him/her for safety reasons, the study Principal Investigator should be notified and the REB/EC should be informed within ten (10) working days.

